1.4 UBLITUXIMAB AND UMBRALISIB (U2) COMBINATION

A Phase I/Ib dose escalation study (Study UTX-TGR-103) was conducted in B-cell (CLL and NHL) malignancies to establish the MTD of the combination of ublituximab and umbralisib (U2) and characterize safety and efficacy (NCT02006485). The study Is completed. The MTD was not reached and the most common all grade, all causality AEs in > 20% of subjects were: diarrhea (57%), nausea (53%), fatigue (43%) and neutropenia (32%) (Davids et al., 2017). The ORR for the CLL/SLL cohort was 62% in the 21 evaluable subjects with a 10% CR rate (Lunning et al., 2019). U2 was well tolerated and the safety and efficacy profile supports further research with multi-drug regimens including novel targeted agents.

The Phase 3 UNITY-CLL trial (NCT02612311) demonstrated that ublituximab and umbralisib (U2) prolonged PFS compared to the chemoimmunotherapy combination of obinutuzumab and chlorambucil in both treatment naïve and previously treated CLL populations (Gribben et al., 2020). The safety profile of the U2 combination was consistent with the profiles seen with umbralisib and ublituximab as monotherapies, and no new safety signals were identified. An interim analysis evaluated the individual contribution of umbralisib and ublituximab as single agents to the U2 combination and confirmed U2 as superior compared to either agent as a monotherapy. These data establish U2 as superior to chemoimmunotherapy; thus, making U2 an appropriate control arm in both treatment naïve and previously treated CLL.

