1.6 RATIONALE/HYPOTHESIS FOR U2 + VENETOCLAX COMBINATIONS

While venetoclax therapy is highly active in patients with CLL/SLL, relapses occur. Additionally, the majority of patients only achieve a PRs to currently available venetoclax combinations. Further, a practical limitation exists with the TLS risk mitigation strategy required for venetoclax administration, which requires intensive monitoring for patients at medium and high risk of TLS and makes administration challenging in the community setting. We hypothesize that the addition of venetoclax following U2 induction will provide deeper levels of remission than have been achieved with single-agent umbralisib, ublituximab, and venetoclax to date. Further, the sequential strategy has been designed to mitigate the risk of venetoclax related TLS by utilizing a debulking course of U2 prior to initiation of venetoclax. Lastly, sequential monitoring for rate of undetectable MRD will be used to potentially inform future time limited therapies based on the achievement of early optimal response.

Based on the above, we propose this Phase 2/3 trial to evaluate U2 with venetoclax (U2-V) and also to compare the U2 regimen in a randomized fashion to the triplet regimen of U2-V.

The combination of U2-V has been evaluated in an ongoing Phase 1 study (NCT03379051) in patients with relapsed or refractory CLL, which supports the dosing regimen used in this study U2-VEN-207. Of 43 patients treated to date, Grade ≥ 3 AEs were infrequent with neutropenia (21%), leukopenia (12%), and IRRs (7%) occurring in over 5% of patients (Barr et al., 2020). Discontinuations due to AEs were also uncommon with 9% and 4% discontinuing umbralisib and venetoclax respectively. No DLTs were observed during the Phase 1 portion, and the RP2D was found to be umbralisib 800 mg QD, ublituximab 900 mg, and venetoclax at standard dosing. The Phase 1 study utilized a 3 Cycle debulking schedule for U2, similar to this Protocol U2-VEN-207. After 3 cycles of U2 debulking, there was an 81% relative reduction in high- and medium-risk TLS, and no patients developed clinical or laboratory TLS during venetoclax administration. Of 27 patients evaluable at Cycle 12, the triple combination of U2 plus venetoclax produced a 100% ORR, 41% CR, and high rates of uMRD in the peripheral blood (96%) and BM (77%). The findings of the Phase 1 study support continued investigation in the current trial.

U2-VEN-207

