²⁰ To be drawn pre-dose C1D1, during Cycle 4, Cycle 12, and approximately every 6 cycles thereafter until Cycle 24. Subjects that end treatment prior to Cycle 24 should continue to have T/B/NK collected until month 24.

²¹ TLS risk assessment according to Section 8.5.3.1 at baseline and on Day 1 of Cycle 4, prior to first dose of venetoclax.

²² Response assessment at baseline (within 30 days prior to Cycle 1 Day 1), and within 14 days prior to Cycles 4 & 12, and at least every 12 cycles thereafter. Radiologic assessment should include CT with contrast or MRI imaging of neck, chest, abdomen, and pelvis. A post-baseline BM biopsy is required to confirm potential CR.

²³ MRD at Cycle 6 for all subjects without signs of clinical progression, perform MRD testing by PB; repeat every 6 cycles. At Cycle 12, MRD by PB will be performed. Subjects in a ≥PR and who are MRD negative by PB, perform MRD testing in BM (central lab). If MRD BM positive, repeat MRD by BM (central lab) is required. Any subject in a CR before Cycle 12 who are MRD negative by PB, perform MRD testing in BM (central lab). If MRD BM positive, repeat MRD by PB should continue every 6 cycles. Subjects that end treatment prior to Cycle 24 should continue to have MRD collected through cycle.

²⁴ and every 6 cycles thereafter in LTFU. See laboratory manual for collection, processing and shipment instructions. 24 Ublituximab to be administered C1 D1, 2, 8 & 15, then D1 C2-6. After C6 no further ublituximab will be administered. 25 See Section 8.0 Treatment Plan for details on umbralisib administration based on treatment status and MRD status.

U2-VEN-207

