11.3 ANALYSIS POPULATION

The safety population will consist of all subjects who received at least one dose of study drug (ublituximab, umbralisib, or venetoclax). For the Phase 2 component, the ITT population will consist of all subjects who received at least one dose of each study drug (ublituximab, umbralisib, and venetoclax).

U2-VEN-207

For Phase 3, the ITT population will consist of all randomized subjects, regardless of administration of study treatment. Analyses of this population will assign subjects the treatment they were scheduled to receive, regardless of any errors of dosing or dose modifications. Subjects who received treatment in the group that is different from what they have been randomized to, will be noted in the clinical study report. The ITT population is the primary analysis population for efficacy analyses.

The per protocol population will include all ITT subjects without major protocol violations. Major protocol violations will be documented. Analyses based on per protocol population may be performed.

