11.8 EFFICACY ANALYSES

Each subject will be assigned to one of the following categories: 1) CR (including CRi), 2) PR, 3) PR-L, 4) SD, 5) PD, 6) early death from malignant disease, 7) early death from toxicity, 8) early death because of other cause, or 9) unknown (not assessable, insufficient data).

Many of the efficacy measures will be based on disease assessments. The best clinical response as well as disease progression may be assessed by an IRC. Definitive disease progression will be based on standard criteria (Hallek et al., 2018) occurring for any reason (e.g., increasing lymphadenopathy, organomegaly or bone marrow involvement; decreasing platelet count, hemoglobin, or neutrophil count; or worsening of disease-related symptoms) other than treatment-related lymphocytosis.

U2-VEN-207

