11.11.1.2 COMPLETE RESPONSE RATE (PHASE 2)

CR rate is defined as the percent of subjects who achieve a CR or CRi. Estimated CR rate with exact 95% confidence interval based on Clopper-Pearson method will be presented for the Phase 2 component.

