11.11.2 SECONDARY EFFICACY OUTCOMES

11.11.2.1 MINIMAL RESIDUAL DISEASE NEGATIVITY

The MRD negativity rate is defined as the proportion of subjects who achieve MRD negative status post-baseline. Subjects who do not have an MRD assessment at any post-baseline visits will be considered non-responders and will be included in the denominator when calculating MRD negativity rate. Estimated MRD negativity rate with exact 95% confidence interval based on Clopper-Pearson method will be presented for the Phase 2 component, while the Phase 3 will utilize a Cochran-Mantel-Haenzel (CMH) test stratified by the randomization factors.

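### The Phase 2 ITT set requires a dose of all three drugs, but venetoclax starts only at Cycle 4, so failures in the 84-day U2 lead-in leave the CR rate and ORR denominators

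*Combined protocol and SAP*

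**What the plan says.** Section 11.3 of the protocol gives one label two meanings.

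- Phase 2: "For the Phase 2 component, the ITT population will consist of all subjects who received at least one dose of each study drug", with all three drugs listed.
- Phase 3: all randomized subjects, treated or not.

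The same section adds: "The ITT population is the primary analysis population for efficacy analyses". The per protocol set is a subset of ITT. The safety population (any dose of any study drug) is assigned to safety analyses in section 11.9.

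CR rate and ORR are the Phase 2 primary objectives (section 2.1). Section 11.11.1.2 reads "Estimated CR rate with exact 95% confidence interval based on Clopper-Pearson method will be presented for the Phase 2 component", and section 11.11.1.3 treats ORR the same way. Neither names a population.

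The Phase 2 dosing schema (section 8.2, Table 9) gives only ublituximab and umbralisib in Cycles 1 to 3 and adds venetoclax in Cycle 4. The footnote to Table 4 in section 5 confirms the timing by placing the tumor lysis risk assessment "at baseline and on Day 1 of Cycle 4, prior to first dose of venetoclax".

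Two other rules bear on the denominator. Section 11.8 gives each subject a response category, and the list includes "early death from malignant disease, 7) early death from toxicity, 8) early death because of other cause" as well as an unknown category. Section 11.11.2.1 says: "Subjects who do not have an MRD assessment at any post-baseline visits will be considered non-responders and will be included in the denominator".

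**The concern.** Membership of the Phase 2 ITT set depends on something that happens after enrollment: staying on study long enough to receive venetoclax. That is not intention-to-treat. The subjects removed are those who did not get through the lead-in, and they are less likely to be responders than those who did.

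The synopsis describes U2 as induction before venetoclax, and section 1.6 describes it as a debulking course chosen to reduce the risk of tumor lysis. Induction failures therefore belong in the response rate of the regimen. Leaving them out means the primary estimates and their exact intervals describe only subjects who reached Cycle 4. The synopsis also cites initial Phase 2 results as part of the basis for starting Phase 3.

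**Working it through.** **Who is excluded.** Cycle length is 28 days (section 8.1), so the lead-in is 3 × 28 = 84 days and Cycle 4 Day 1 is study day 85. Anyone who stops all treatment on days 1 to 84 cannot have received venetoclax. A subject who stays on U2 but never starts venetoclax is also excluded. Stopping only ublituximab or umbralisib does not by itself exclude a subject, because sections 8.5.2.2 and 8.5.4 allow the remaining drugs to continue.

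**Direction.** Let L be the share of dosed subjects lost before venetoclax, p_R the response rate in those retained and p_L the rate in those lost.

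- Reported rate = p_R
- All-dosed rate = (1 − L) × p_R + L × p_L
- Bias = L × (p_R − p_L)

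The bias is upward whenever the lost respond less often than the retained. For CR this is almost certain if any subjects are lost, because a CR needs marrow confirmation and few early leavers would have one. For ORR it is very likely. The first post-baseline scan falls within 14 days before Cycle 4 (section 5), so a subject can have a PR or PR-L recorded and then leave, which offsets part of the ORR bias.

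**Size.** The plan states no early-loss figure, so there is nothing to reproduce; L of 5 to 15% is an assumption. For p_R, section 1.6 reports: "Of 27 patients evaluable at Cycle 12, the triple combination of U2 plus venetoclax produced a 100% ORR, 41% CR". So p_R = 1.00 for ORR and 0.41 for CR. For p_L there are two cases: no response among those lost, or response at the U2-only rates in section 1.4 ("The ORR for the CLL/SLL cohort was 62% in the 21 evaluable subjects with a 10% CR rate").

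Bias in percentage points:

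| L | ORR, p_L = 0 | ORR, p_L = 0.62 | CR, p_L = 0 | CR, p_L = 0.10 |
|---|---|---|---|---|
| 5% | 5.0 | 1.9 | 2.05 | 1.55 |
| 10% | 10.0 | 3.8 | 4.10 | 3.10 |
| 15% | 15.0 | 5.7 | 6.15 | 4.65 |

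For example, at L = 10% the ORR bias is 0.10 × (1.00 − 0.62) = 3.8 points, and the CR bias is 0.10 × (0.41 − 0.10) = 3.1 points.

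**Exact (Clopper-Pearson) 95% intervals with 10% lost:**

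| Cohort | Endpoint | Three-drug set | All dosed, none of the lost respond |
|---|---|---|---|
| 60, 6 lost | ORR | 54/54 = 100% (93.4–100) | 54/60 = 90.0% (79.5–96.2) |
| 60, 6 lost | CR | 22/54 = 40.7% (27.6–55.0) | 22/60 = 36.7% (24.6–50.1) |
| 30, 3 lost | ORR | 27/27 = 100% (87.2–100) | 27/30 = 90.0% (73.5–97.9) |

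If half of the 6 lost had responded, the ORR would be (54 + 3)/60 = 95.0% (86.1–99.0).

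**Against the plan's other rules.** Section 11.8 has categories for early death and unknown response, and section 11.11.2.1 keeps subjects without an MRD assessment in the denominator. Under section 11.3, lead-in deaths and unassessed lead-in subjects are removed before either rule can reach them.

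**The case against.** - **The link to CR and ORR is inferred.** The sentence making ITT primary closes the Phase 3 paragraph, and sections 11.11.1.2 and 11.11.1.3 name no population. In the copy reviewed, section 11.1 has no text, and section 11 defers detail to a Statistical Analysis Plan whose text does not appear. This stands as a caveat. But the only other efficacy set is a subset of ITT, so the visible plan either uses the three-drug set or leaves the Phase 2 denominator undefined. Both need correction.
- **The objective is the activity of the triplet.** Section 2.1 asks for the rates of the three-drug combination, in a single-arm estimate with no test. That is a legitimate question, but it suits a supportive set under its own name, because the protocol studies the sequence with induction included.
- **Sections 11.8 and 11.11.2.1 do not strictly contradict section 11.3.** Their rules still work for subjects who are lost after the first venetoclax dose. This is fair: they show a different approach to early failures, and the point does not depend on them.
- **The size is weakly anchored.** Section 1.6 reports discontinuation for adverse events of 9% for umbralisib and 4% for venetoclax, which does not support a 15% loss, though those figures cover neither all reasons nor this window. The 100% ORR comes from 27 of 43 relapsed or refractory patients still evaluable at Cycle 12, a more selected group than anyone with one venetoclax dose. The ORR gaps with no response among the lost are therefore ceilings for each assumed loss.
- **A reader could recompute, and the change is late.** Disposition counts (section 11.4) would reveal the exclusion but would not change the primary estimate or its interval. Phase 2 enrollment closed on 29 January 2021 (section 4.1), so the timing of any change must be documented; that is no reason to keep the definition.

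**Conclusion.** The concern holds. As written, the Phase 2 ITT definition excludes every subject who fails or leaves during the 84-day U2 lead-in, and every subject who never starts venetoclax. On the natural reading of section 11.3, this carries into the CR rate and ORR.

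If 5 to 15% are lost, the upward bias is about 2 to 15 points on an ORR near 100% and about 1.6 to 6.2 points on a CR rate near 41%, depending on how the lost subjects respond. These figures rest on an assumed loss rate and on response rates borrowed from other studies. With no losses there is no bias. The definition and its effect on the denominator do not depend on those assumptions. It should be fixed; Phase 3 is unaffected.

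**What to change.** In section 11.3 and the SAP:

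1. Define the Phase 2 primary efficacy population as all enrolled subjects who received any dose of any study drug. This is the safety population the section already defines.
2. State in sections 11.11.1.2 and 11.11.1.3 that this population is the denominator, and that subjects with no documented response count as non-responders, in line with the MRD rule.
3. Keep the three-drug set as a sensitivity population under another name, such as triplet-exposed, and reserve the ITT label for Phase 3.
4. Record when the change was made relative to review of Phase 2 data.

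The cost is a wording amendment, which goes to the IRB under section 15.3, and matching SAP text. No new data are needed, since the added subjects are already in the safety population. The reported Phase 2 rates are likely to be somewhat lower.

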11.4 SUBJECT DISPOSITION

Subject disposition summaries will include the number and percentage of enrolled/randomized subjects in the safety, ITT, and per protocol populations. The summaries will also include the reasons for permanent discontinuation of study treatment and study.

11.5 SUBJECT DEMOGRAPHICS AND BASELINE CHARACTERISTICS

Baseline demographic and clinical characteristics will be summarized as percentages for categorical variables and as mean, standard deviation, median, minimum and maximum for continuous measures. The analyses of baseline characteristics will be performed for the ITT population.

11.6 MEDICAL HISTORY

Medical history will be captured at the screening visit. Medical history will be coded using MedDRA and will be summarized by MedDRA system organ class and preferred term for the safety population.

11.7 EXTENT OF EXPOSURE

The dose (mg) of study drugs administered, the total number of doses of study drugs, and the duration of treatment (number of study cycles) will be summarized with descriptive statistics. The number and percentage of subjects whose dose is modified at any time will be summarized by each type of modification by cycle and overall.

11.8 EFFICACY ANALYSES

Each subject will be assigned to one of the following categories: 1) CR (including CRi), 2) PR, 3) PR-L, 4) SD, 5) PD, 6) early death from malignant disease, 7) early death from toxicity, 8) early death because of other cause, or 9) unknown (not assessable, insufficient data).

Many of the efficacy measures will be based on disease assessments. The best clinical response as well as disease progression may be assessed by an IRC. Definitive disease progression will be based on standard criteria (Hallek et al., 2018) occurring for any reason (e.g., increasing lymphadenopathy, organomegaly or bone marrow involvement; decreasing platelet count, hemoglobin, or neutrophil count; or worsening of disease-related symptoms) other than treatment-related lymphocytosis.

U2-VEN-207

11.9 SAFETY ANALYSES

Safety analyses will be performed using the safety population. Safety analyses will be primarily based on the incidence, severity, and type of AEs, as well as on clinically meaningful laboratory results, physical examination, and vital signs as available. Safety variables will be tabulated and presented by the dose of ublituximab, umbralisib, and/or venetoclax actually received. Exposure to study treatment and reasons for discontinuation of study treatment will also be tabulated.

Detailed information collected for each AE will be included in a listing: AE term, start/stop dates of the AE, seriousness, severity, relationship to study drug(s), action taken, and outcome. In addition, the number and percentage of subjects experiencing at least one treatment-emergent AE will be tabulated by body system, preferred term, and CTCAE grade. Treatment-emergent AEs, drug-related AEs, AESIs, SAEs, AEs with a fatal outcome, and AEs leading to discontinuation/dose modification will be further summarized. Summary statistics for actual values and for changes from baseline will be tabulated for clinical laboratory results by scheduled visit. Subjects with laboratory values outside of the normal reference range at any post-baseline assessment will be summarized and graded per NCI CTCAE Version 5.0 as applicable. Subject incidence of abnormal laboratory results will be summarized by treatment group and maximum grade for each abnormal laboratory finding.

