			mg daily 400 mg daily					

U2-VEN-207

Cycles 7 - 15					
Ublituximab Umbralisib Venetoclax					
Day 1 of Cycle 9, Cycle 12, and Cycle 15	Days 1 - 28	Days 1 - 28			
900 mg	800 mg daily	400 mg daily			

Phase 3: Arm B (U2) Randomized Subjects					
	Cycle 1				
Ublituximab			Umbralisib		
Day 1	Day 2	Day 8 & 15	Days 1 - 28		
150 mg	750 mg	900 mg	800 mg		
	Cycles 2 - 6				
1	Jblituximab	Umbralisib			
Day 1			Days 1 - 28		
900 mg		800 mg			
	Cycle 7+				
Ublituximab			Umbralisib		
Day 1, every 3 cycles (9, 12, 15, 18, etc.)		Days 1 - 28			
900 mg		800 mg			

Study Drugs

Ublituximab is an investigational, recombinant chimeric monoclonal antibody against the CD20 antigen, available as a 25 mg/mL concentrate for solution for infusion, supplied by TG Therapeutics, Inc.

Umbralisib is a novel investigational, once daily oral dual inhibitor of PI3K δ and CK1 ϵ available in 200 mg tablets, supplied by TG Therapeutics, Inc.

Venetoclax is an orally administered BCL-2 inhibitor available in 10 mg, 50 mg, and 100 mg tablets, commercially available as VENCLEXTATM.

LIST OF ABBREVIATIONS

Abbreviations and Definitions of Terms				
ADCC	antibody-dependent cellular cytotoxicity			
ADCP	antibody-dependent cellular phagocytosis			
ADL	activities of daily living			
AE(s)	adverse event(s)			
AESI	adverse event of special interest			
AKT	protein kinase B			
ALC	absolute lymphocyte count			
ALT	alanine aminotransferase			
AST	aspartate aminotransferase			
ATP	adenosine triphosphate			
AUC	area under the curve			
BCG	Bacille Calmette Guerin			
BCL-2	B-cell lymphoma 2			
ВН	BCL-2 homology			
BM	bone marrow			
BTK	bruton's tyrosine kinase			
BUN	blood urea nitrogen			
C, c	Cycle			
Ca	calcium			
CBC	complete blood cell count			
CD	cluster of differentiation			
CDC	complement-dependent cytotoxicity			
CK1E	casein kinase 1 epsilon			
CL	clearance			
CLL	chronic lymphocytic leukemia			
Cm	centimeter			
Cmax	maximum concentration			
CMV	cytomegalovirus			
CNS	central nervous system			
CO ₂	carbon dioxide			
CR	complete response			
CRi	complete response incomplete			
CRO	Contract Research Organization			
CT	computed tomography			
CTCAE	Common Terminology Criteria for Adverse Events			
CVA	cerebrovascular accident			
D, d	day/Day			
DLBCL	diffuse large B-cell lymphoma			
DLT	dose limiting toxicity			
DNA	deoxyribonucleic acid			
DOR	duration of response			
DRG	data review group			
DSMB	Data Safety Monitoring Board			
EC	ethics committee			

U2-VEN-207

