8 TREATMENT PLAN

8.1 TREATMENT SUMMARY

Treatment will be administered in 28-day cycles. Patients must continue to meet eligibility in respect to adequate organ system function as per Inclusion Criteria #2 on Cycle 1 Day 1. Hematology and chemistry results must be reviewed prior to dosing on Cycle 1 Day 1 to ensure subjects meet Inclusion Criteria #2 as per the protocol.

Please see Section 8.5.3: Guidelines for Administration of Venetoclax for specific information on TLS risk, prophylaxis and assessments.

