12.2.3 ADVERSE EVENT/SERIOUS ADVERSE EVENT RECORDING

All non-serious AEs regardless of relationship to the study drugs are to be recorded on the eCRF from Cycle 1/Day 1 until 30 days after discontinuation or completion of protocol-specific treatment. Immune-related AE (irAEs) are to be recorded on the eCRF from Cycle 1/Day 1 until 90 days after study discontinuation or completion of protocol-specific treatment. All AEs must include the Investigator's assessment of the event's seriousness, severity, and causality to study drug.

All serious AEs (i.e. SAEs) regardless of relationship to the study drug(s) are to be recorded on the eCRF and the SAE Report Form from signing of informed consent until 30 days after discontinuation or completion of protocol-specific treatment. Immune-related SAEs (irSAEs) are to be recorded on the eCRF and SAE Report Form from signing of informed consent until 90 days after study discontinuation or completion of protocol-specific treatment. All SAEs must include the Investigator's assessment of the event's seriousness, severity, and causality to study drug.

If an AE is deemed by the Investigator as serious, as per the SAE criteria, it should be reported **as soon as possible and no later than 24 hours** of awareness to the Sponsor or designee using the SAE Report Form and recorded within the same timeframe on the eCRF. Follow-up information for SAEs and information on non-serious AEs that become serious should also be reported **as soon as possible but no later than 24 hours** to the Sponsor or designee using the SAE Report Form and recorded on the eCRF. SAEs should be followed until resolution (including results of an autopsy report, if applicable). The Investigator must review and sign off on the data on the SAE Report Form

U2-VEN-207

and transmission of the SAE Report Form should be confirmed by the site personnel submitting the form.

Disease progression or death due to disease progression should be reported by the Investigator as a SAE **only** if it is assessed that the study drugs caused or contributed to the disease progression (i.e., by a means other than lack of effect). Unrelated events of CLL/SLL progression should be captured on the appropriate eCRF and not on the AE eCRF.

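### Section 11.9 relies on crude AE percentages although Arm A stops at Cycle 15 and Arm B is open-ended, so U2-V can look safer per unit time for events that accrue on treatment

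*Combined protocol and SAP*

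**What the plan says.** **Safety measure.** Section 11.9 opens its analysis plan with "Safety analyses will be primarily based on the incidence, severity, and type of AEs", and specifies that "the number and percentage of subjects experiencing at least one treatment-emergent AE will be tabulated by body system, preferred term, and CTCAE grade". It adds: "Exposure to study treatment and reasons for discontinuation of study treatment will also be tabulated". Section 11.7 treats exposure in the same descriptive way: "the duration of treatment (number of study cycles) will be summarized with descriptive statistics". The supplied text contains no person-time rate, time-to-first-AE analysis or common-window AE table.

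**Treatment length.** Section 8.1: "Treatment will be administered in 28-day cycles". In the synopsis dosing tables (repeated as Tables 10 and 11), Arm A's last block is Cycles 7 to 15, with ublituximab on "Day 1 of Cycle 9, Cycle 12, and Cycle 15". Arm B's last block is Cycle 7+, with ublituximab on "Day 1, every 3 cycles (9, 12, 15, 18, etc" and no final cycle. Section 4.1 ends treatment at definitive progression, completion, unacceptable toxicity or withdrawal; only Arm A has a scheduled completion. Section 10.1 leaves completion out of its own list, and the two lists should be reconciled.

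**AE recording.** Under Section 12.2.3, non-serious AEs "are to be recorded on the eCRF from Cycle 1/Day 1 until 30 days after discontinuation or completion of protocol-specific treatment". SAEs also stop at 30 days, and immune-related events at 90 days. After that, only events that the investigator judges drug-related are reported. The Phase 3 schedule (Table 5) marks no AE assessment in long-term follow-up.

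**The concern.** AE recording follows treatment, and treatment length differs between the arms by design. A subject in Arm B who stays progression-free has longer to record a first event than any subject in Arm A. Two regimens with the same event rate on treatment would then show different crude percentages. The better U2 controls the disease, the wider the gap.

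Venetoclax is the only added drug, and describing the safety of the regimens is a Phase 3 objective (Section 2.1). The DSMB has benefit/risk oversight (Section 13.1), and Section 11.11.3 foresees submission to health authorities. Readers will set the two columns side by side whether or not a test is planned. The plan allows for time at risk in PFS, through Kaplan-Meier, log-rank and Cox methods (Section 11.11.1.1), but not in the AE tables.

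**Working it through.** The plan gives no AE rate or safety power, so there is no figure of its own to reproduce.

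**1. Maximum routine window, Arm A (document figures)**
- Treatment: 15 × 28 = 420 days; 420 / 30.44 = 13.8 months.
- Routine AE window: 420 + 30 = 450 days; 450 / 30.44 = 14.8 months. For immune-related events: 420 + 90 = 510 days.
- Arm B: no maximum.

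**2. Simulated windows**

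Inputs from the documents: 24-month accrual (Section 4.4), 1:1 allocation, and data cuts set by event fractions (Sections 4.1 and 11.11.3).
- Naïve cohort: final 172/400 = 43%; interim 115/400 = 29%.
- Previously treated cohort: final 122/300 = 41%; interim 82/300 = 27%.

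Assumptions not in the documents: uniform accrual; exponential PFS with U2 median 20, 30 or 40 months; PFS hazard ratio 0.61; other discontinuation 0 or 2% per month; constant AE hazard h of 0.5% to 4% per month, the same in both arms.

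Formulas:
- Treatment time = min(PFS, other discontinuation), capped at 13.8 months in Arm A.
- Window w = min(treatment time + 30 days, data cut − entry).
- Crude percentage = mean of 1 − exp(−h·w).
- Break-even ratio k solves mean[1 − exp(−k·h·w_A)] = mean[1 − exp(−h·w_B)].

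Naïve cohort, final analysis, equal hazards of 2% per month:

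| U2 median PFS | Other discontinuation | Crude %, A vs B |
|---|---|---|
| 20 months | 0 | 21.8 vs 25.0 |
| 30 months | 2% per month | 21.0 vs 28.0 |
| 40 months | 0 | 24.0 vs 42.5 |

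Mean AE window, Arm B divided by Arm A:

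| Analysis | Range of ratio |
|---|---|
| Naïve, final | 1.15 (12.8 / 11.1 months) to 2.16 (29.8 / 13.8 months) |
| Previously treated, final | 1.12 to 2.04 |
| Both cohorts, interim | 1.03 to 1.47 |

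With equal constant hazards, Arm A's crude percentage was lower in every final-analysis scenario. Across the naïve-cohort final scenarios and hazards, k ran from 1.09 to 2.13.

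**3. Where the effect fades or is outweighed** (naïve final, U2 median 30 months, 2% per month discontinuation)
- Events confined to the first 6 months, equal hazards: 10.6% (A) vs 10.4% (B) at 2% per month, and 24.3% vs 23.9% at 5% per month. There is almost no bias.
- Arm A hazard 1.25 times Arm B's: 25.5% vs 28.0%. Arm A still looks better.
- Arm A hazard 1.5 times: 29.6% vs 28.0%. The excess shows, but is much reduced.
- Arm A hazard doubled: 37.1% vs 28.0%. Arm A clearly looks worse.

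**The case against.** **The tables are descriptive, and detail is deferred.** Section 11.9 plans no between-arm AE test, the objective is to characterise safety, and Section 11 leaves detail to a SAP whose safety text is not supplied. All true, and adjusted tables may be planned there. But Section 11.9 already names its main measure, and naming the time-matched summary now avoids choosing it after the data are seen.

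**Whole-regimen incidence answers a real question.** Limited treatment duration is part of the trial's rationale, so a lower total AE burden from stopping at Cycle 15 is a genuine property of U2-V. This stands, and it is why the crude table should stay. It does not show what happens per unit of time on treatment.

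**There is partial mitigation.** Exposure is tabulated, laboratory values are summarised by scheduled visit, and drug-related events are still reportable after the 30- or 90-day window. But separate exposure tables do not adjust a percentage, and late reporting depends on the investigator's attribution in an open-label trial.

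**Stronger readings that the documents do not support.**
- A reader might infer that U2-V will look safer in every AE table. Venetoclax ramp-up starts at Cycle 4, so tumour lysis during ramp-up, like early infusion reactions, falls well inside Arm A's window. A large enough excess hazard would also show.
- A reader might fix Arm B at 2 or 3 years for every subject. With equal hazards of 0.05 to 0.3 per year this gives crude A/B ratios of 0.60 to 0.67 or 0.42 to 0.51. No document states those durations, and the calculation ignores progression, dropout and staggered entry. The 3-year case implies a window ratio of (3 × 365.25 + 30) / 450 = 2.50, beyond every scenario simulated.
- A reader might expect the early DSMB reviews to be distorted. Meetings every 6 to 9 months begin before Arm A can reach Cycle 15, while the windows are still similar.

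**Conclusion.** The concern holds for events that accrue with time on treatment. The unequal windows follow directly from the dosing tables and Section 12.2.3, and the supplied safety text does not allow for them. The size is not fixed by the documents. It rests on assumed PFS, discontinuation and constant AE hazards, and the effect can be modest (U2 median PFS 20 months with dropout) or large (40 months without). It is smaller at the interims and close to nil for early events. This is a gap in what the tables can show, not evidence that U2-V's toxicity will be hidden. It is a worthwhile and cheap improvement.

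**What to change.** Keep the crude whole-regimen table. In Section 11.9 and the SAP add, by arm within each cohort, for TEAEs, Grade 3 or higher AEs, SAEs, AESIs and AEs leading to discontinuation:

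1. **Main time-matched summary:** cumulative incidence of first event from Cycle 1 Day 1 to a fixed study day, Day 450 (end of Cycle 15 plus 30 days). Censor at data cut, and treat death and the end of the subject's AE recording window as competing events.
2. **Supportive:** exposure-adjusted incidence rates per 100 patient-years with 95% CIs. State that they assume a constant hazard and can penalise the shorter regimen for early events, so they should not stand alone.

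Cost: a paragraph of text and a few extra tables. AE start and stop dates (Section 11.9) and dosing dates (Sections 8.5.1.3 and 8.5.2.1) are already recorded. The limits are that item 1 says nothing about Arm B after Day 450, which the crude table still covers, and that item 2 carries its constant-hazard assumption.
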